Study Protocol

Version 3

1 September 2018

Title:

A prospective double-blinded randomized controlled trial: assessment of immediate post-operative pain for FiLAV versus LIFT in the treatment of trans-sphincteric anal fistulas (LASERLIFT)

Design

A prospective, double-blinded, single credentialed colorectal surgeon, randomised controlled trial.

Settings

University Malaya Medical Centre, a tertiary teaching hospital.

Patients

Patients with high transsphincteric anal fistulas from January 2018 to December 2020

Intervention

Laser versus ligation of the fistula tract (LIFT) treatment

Primary Outcome Measure

Pain scores at rest and movement, at 6 and 24 hours post operatively will be measured using the visual analogue scale (VAS)

Secondary Outcome Measures

1. Operative time was measured in minutes at 0-, 3- and 6-months post-surgery
2. Continence assessed using Wexner at 0-, 3- and 6-months post-surgery
3. Quality of life assessed using SF-36 questionnaire at 0, 3 and 6 months post-surgery

Study Participants

Written informed consent was obtained from all patients all patients with high transphincteric anal fistulas were recruited into this trial.

Inclusion Criteria:

1. 18 – 75years
2. Able to give consent
3. Complex transphincteric fistulas; high transphincteric fistula, involving >30% of the external anal sphincter; Multiple fistulas; Anterior fistulas; Recurrent fistulas; Fistulas with seton

Exclusion Criteria:

1. Active perianal sepsis requiring drainage
2. Fistulas of non-cryptoglandular origin
3. - Crohn's, TB, malignancy
4. Expected lifespan <6 months
5. Pregnant women
6. Patient's with more than 1 definitive surgery done for the fistula before
7. Patient's with human immunodeficiency virus infection
8. Patient's with pre-existing chronic pain disorders
9. Patient's with Non-steroidal Anti-inflammatory Drug (NSAIDS) / Paracetamol allergies

All patients' will be recruited from the surgical outpatient clinic at UMMC, where thorough history and clinical examination will be performed. Next patient will undergo an endo-anal ultrasound (EAUS - 2052 probe, GE healthcare BK Medical) by an experienced operator which then confirms the presence of a high transphincteric fistula and/or other branching tracts as per Park's fistula classification. An MRI would only performed if the EAUS was inconclusive. Baseline assessment of quality of life (QOL) using the SF36 questionnaire and continence using Wexner's scale will be done at the start upon recruitment. Patients will randomised into the laser or ligation arm using block randomisation via the Sealed Envelope program (<https://www.sealedenvelope.com>). Double blinding was achieved as patients and the data collector were blinded to the interventions.

Study Intervention And Post-Intervention Care

The laser procedure will be performed according to the technique described by Wilhelm et al. The internal and external opening will first be identified and the tract debrided. Upon activation a laser fibre (10Watt, 600nm, fibreglass length 1800nm, emitting a wavelength of 1470 nm, ENDOTEQ Medical Laser Germany GmbH) will release thermal energy of maximum 100 Joules homogeneously into the tract while being withdrawn at the speed of 1mm/s. The internal orifice was then closed with an interrupted absorbable stitch. For cases which required a core out, the external opening then left open to heal by secondary intention.

The LIFT procedure would be performed as first described by Rojanasakul et al 2007. The internal and external opening was first identified. A curvilinear incision made at the intersphincteric plane after identification of the internal and external opening. Dissection was then performed up until where the tract was encountered where it was then ligated as close as possible to the internal opening and a portion of the tract excised. The external opening was then curetted and tissue sent for histopathology studies. The skin then closed loosely with an interrupted absorbable suture.

Standardised analgesia (PO Celecoxib 40mg and PO Paracetamol 1g) will be served at exactly 6 hours post operatively. Pain scores was assessed by a blinded healthcare professional using the visual analogue scale (VAS) at 6 hours and 24 hours post operatively, at rest and on movement.

Upon discharge, patients would be given oral antibiotics, PO celecoxib 40mg BD and PO paracetamol 1g QID for a week duration. All patients were reviewed at one week post-op for a wound assessment, and an official surgical consult at 1 month and 6 months post operatively.

Each surgical consult involved a history taking, clinical examination, QOL and continence assessment. Should there be any suspicion of a recurrence before 6 months they will be subjected to an EAUS. An MRI will be performed if the EAUS is inconclusive.

Study Definitions And Outcome Measures

Successful fistula healing is defined as complete wound healing and closure of all the external openings in combination with the cessation of outflow from the external openings at 6 months post operatively. Surgical failure was defined as failure of the fistula to close with persistence of discharge at 6 months post operatively. This encompassed the spectrum of wound infection, recurrence and technical failure.

Sample Size Justification

As there were no prior studies with the primary outcome on pain score prior to trial commencement, we proceeded to calculate the sample size based on the score obtained from a local audit. Then using the G-power software, to achieve an alpha error of 5%, confidence interval of 95%, power of 0.9 and a large effect size, 28 fistulas were required per arm.

Statistical Analysis

Analysis would be performed using SPSS Statistics for Mac (version 23 Inc., Chicago, IL, USA) with an intention-to-treat basis. Continuous variables will be presented as median and range or mean and standard deviation. Differences between groups can be compared using chi-square analysis or the Fisher exact test when data is categorical. While continuous variables can be compared using the student t-test or Mann-whitney based on normality of data distribution. We will consider data to be statistical significance if $p < 0.05$.

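### Four VAS pain scores are jointly primary with no lead score, adjustment or success rule, so the stated 5% alpha and 90% power are not both assured

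*Combined protocol and SAP*

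**What the plan says.** The Primary Outcome Measure section reads "Pain scores at rest and movement, at 6 and 24 hours post operatively will be measured using the visual analogue scale (VAS"). That is a two-by-two set: rest and movement, each at 6 h and 24 h. Study Intervention And Post-Intervention Care repeats it: "visual analogue scale (VAS) at 6 hours and 24 hours post operatively, at rest and on movement".

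Sample Size Justification contains one calculation, based on an unspecified score from a local audit. It cites "alpha error of 5%, confidence interval of 95"% and "power of 0.9 and a large effect size, 28 fistulas were required per arm". It does not say which of the four scores it concerns, what the numerical effect size is, or whether the test is one- or two-sided.

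Statistical Analysis says that "continuous variables can be compared using the student t-test or Mann-whitney based on normality of data distribution", and then "We will consider data to be statistical significance if $p < 0.05". No section gives a lead score, a composite or repeated-measures summary, a testing order, a multiplicity adjustment, or a rule for how many scores must be significant.

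**The concern.** Four primary scores and one calculation for one score do not fit together unless the plan says how the four combine into a conclusion. Separate tests at p<0.05 are the natural reading, although the plan does not say so. Two success rules are then open:

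- **Any one score suffices.** The chance of a false claim exceeds 5%.
- **All four are required.** The 5% holds, but power is below that of a single test.

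Immediate post-operative pain is the purpose in the trial's title, so this bears on the headline conclusion. If one to three of the four scores are significant, whether the trial is positive can be settled after the results are known.

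**Working it through.** **Inputs from the documents:** four scores, alpha 0.05, power 0.90, 28 per arm in two equal arms, t-test or Mann-Whitney.

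**Assumptions:** standardised effect d = 0.8 for a large effect (or the d that makes 28 per arm exact); equal effects on all four scores; equal pairwise correlation from 0 to 0.9; normal data; t-tests; 28 independent patients per arm. The documents count fistulas and give no correlation.

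**1. Reproduce the 28.** For one two-sample t-test, power comes from the noncentral t with 2n − 2 = 54 degrees of freedom and noncentrality d√(n/2). With d = 0.8 and n = 28 this is 0.8 × √14 = 2.99.

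- One-sided: required n = 27.5, rounded up to 28. Power at 28 is 90.5%.
- Two-sided: required n = 33.8, rounded up to 34. Power at 28 is 83.6%. For 90% at 28, d must be 0.882.

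So 28 per arm is what a single comparison needs, either one-sided at d = 0.8 or two-sided at d = 0.88. It makes no allowance for four.

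**2. Any-one rule, no true effect.** With independent scores the false-positive rate is 1 − 0.95⁴ = 18.5%. With correlated scores it was simulated (100,000 trials per setting, 28 per arm):

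| Correlation | Two-sided | One-sided |
|---|---|---|
| 0 | 18.6% | 18.6% |
| 0.5 | 15.6% | 14.4% |
| 0.7 | 13.2% | 12.2% |
| 0.9 | 9.4% | 8.8% |

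The two-sided rates are 9.4/5 = 1.9 to 18.6/5 = 3.7 times the stated 5%.

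**3. All-four rule, equal true effect on every score.** With independent scores, a 90% single test gives 0.9⁴ = 65.6%. Simulated power with correlation:

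| Correlation | One-sided, d = 0.8 (single test 90.5%) | Two-sided, d = 0.88 (single test 90%) | Two-sided, d = 0.8 (single test 83.6%) |
|---|---|---|---|
| 0.5 | 75.0% | 73.8% | 61.6% |
| 0.7 | 79.0% | 78.1% | 67.1% |
| 0.9 | 84.1% | 83.4% | 74.7% |

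**4. Split results (one to three of four significant), same settings.**

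| Correlation | One-sided, d = 0.8 | Two-sided, d = 0.88 | Two-sided, d = 0.8 |
|---|---|---|---|
| 0.5 | 24.2% | 25.3% | 36.3% |
| 0.7 | 19.0% | 19.7% | 28.4% |
| 0.9 | 11.2% | 11.6% | 16.4% |

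**5. Adjusted testing at 28 per arm.** The first step of Holm uses 0.05/4 = 0.0125. Power for one given score at that level is 75.2% (one-sided, d = 0.8), 76.0% (two-sided, d = 0.88) or 65.9% (two-sided, d = 0.8). The chance that at least one score is rejected is higher:

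| Correlation | One-sided, d = 0.8 | Two-sided, d = 0.88 | Two-sided, d = 0.8 |
|---|---|---|---|
| 0.5 | 95.1% | 95.5% | 91.1% |
| 0.7 | 91.5% | 92.0% | 85.9% |
| 0.9 | 85.1% | 85.7% | 77.7% |

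**6. Sample size for an all-four rule at 90%,** if the single test has 90% at 28: about 39 per arm at correlation 0.5, 37 at 0.7 and 33 to 34 at 0.9.

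Simulation error is about 0.1 to 0.2 percentage points.

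**The case against.** The strongest reply is that the plan adopts neither rule. It says only how variables can be compared, so the error and power figures describe hypothetical readings and the defect is an unspecified rule. That is right, and the figures are conditional. But a plan without a rule cannot claim the 5% and the 90% together, and for any correlation below 1 the direction under each reading is fixed.

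A second reply is that keeping four scores need not be costly. Holm with a claim on at least one score holds 5% and gives about 96% and 92% power at correlations 0.5 and 0.7, without extra patients, where a single test has 90%. This also stands, with limits. It requires equal effects on all four scores, it falls to about 86% at correlation 0.9, and the plan states no such rule.

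A third is that effect size, equal effects, correlation and normality all come from outside the documents. They do, which is why ranges are shown. Equal effects at 6 h and 24 h are not a given. High correlation does not remove the problem: at 0.9 the any-one error is still nearly twice 5%.

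Finally, the order of the 6 h VAS and the 6 h analgesia is a measurement matter, separate from multiplicity. It matters here only if a 6 h score is made primary.

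**Conclusion.** The concern holds. The design is sized for one comparison, while the primary outcome contains four and has no rule joining them. An unadjusted any-one rule gives a two-sided false-positive rate of about 9% to 19%. An all-four rule gives about 74% to 84% power at correlations 0.5 to 0.9 where a single test has 90%, and about 62% to 75% if the test is two-sided with d = 0.8. These sizes rest on the assumptions listed in the check. The missing rule is read directly from the text and does not depend on them. Because it can decide the headline conclusion, it should be fixed before any unblinded data are seen.

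**What to change.** Name one of the four scores as the single primary endpoint, at the sponsor's choice, and make the other three secondary. This keeps the 5%, keeps 28 per arm on the plan's own calculation, and changes nothing in data collection. It takes one sentence in Primary Outcome Measure and one in Statistical Analysis. The cost is that three scores lose primary status.

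If a 6 h score is chosen, add a clause on whether VAS is recorded before or after the analgesia, which "will be served at exactly 6 hours post operatively". The documents place both at 6 hours and give no order.

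If all four scores stay primary, state one rule and restate the power for it:

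- **Holm:** state whether power refers to at least one score or to a given score. The first can stay above 90% at 28 per arm under the conditions above; the second is 66% to 76% at the first step.
- **Fixed testing order:** the first score keeps single-test power. Later scores are tested only while each earlier one is significant.
- **All four required:** about 5 to 11 more per arm (33 − 28 = 5 at correlation 0.9; 39 − 28 = 11 at 0.5) to reach 90%, if the single test has 90% at 28.

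### Tract status is known before randomisation but is used in neither the allocation nor the primary VAS comparison, which forgoes precision if tract number predicts early pain

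*Combined protocol and SAP*

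**What the plan says.** The recruitment paragraph that follows the eligibility criteria describes an endo-anal ultrasound that "confirms the presence of a high transphincteric fistula and/or other branching tracts", with MRI if the ultrasound is inconclusive. Baseline quality of life and continence come next, and block randomisation of patients through Sealed Envelope after that. No stratification factor and no block size are given.

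Inclusion criterion 3 admits, besides high transsphincteric fistulas, "Multiple fistulas; Anterior fistulas; Recurrent fistulas; Fistulas with seton". The number of tracts can therefore differ between patients.

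For continuous outcomes, including VAS at rest and on movement at 6 and 24 hours, Statistical Analysis says: "While continuous variables can be compared using the student t-test or Mann-whitney based on normality of data distribution". It names no covariate and no stratified analysis.

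Sample Size Justification specifies a "power of 0.9 and a large effect size, 28 fistulas were required per arm". The effect size is not given as a number, and the unit is fistulas although patients are randomised.

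**The concern.** Tract status is one of the few features of the disease that the plan establishes in every patient before allocation. A patient with several tracts may have more tissue treated and so more pain in the first day. If so, the plan leaves this information unused at both points where it could help.

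Two things would follow. The part of the VAS variation that tract status explains stays in the error term, so the confidence interval is wider than it need be. And in a trial of this size the arms may by chance differ in their share of multiple-tract patients, which moves the observed pain difference in that one trial. Blocking equalises the arm totals but does nothing for tract status. If an imbalance were noticed afterwards and no adjustment had been planned, any adjustment then made would be open to the criticism that it was chosen after seeing the data.

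**Working it through.** **Inputs from the documents.** Alpha 0.05, power 0.90 and 28 per arm (Sample Size Justification). Sidedness, the VAS SD and the audit score are not given, so everything is in SD units.

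**Assumptions, not in the documents.** A large effect is d = 0.8, the conventional value. Share with multiple tracts p = 0.2 to 0.4. Their VAS is higher by g = 0.3 to 1.0 SD, where the SD is that among patients of the same arm and tract status. The 28 are treated as patients.

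**1. The plan's own figure.** Two-sample t-test, noncentral t, d = 0.8, alpha 0.05, power 0.90:
- one-sided: 27.5, so 28 per arm, which matches;
- two-sided: 33.8, so 34 per arm, which does not match.

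At 28 per arm, two-sided power for d = 0.8 is 0.836, and the difference detectable with 90% two-sided power is 0.88 SD. The unstated sidedness is a separate matter. I use the two-sided 0.836 as the baseline below.

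**2. Variance explained by tract status.** R² = p(1−p)g² / (1 + p(1−p)g²). The SE is multiplied by √(1−R²), and the equivalent gain in sample size is 1/(1−R²) − 1.

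| p | g | R² | SE ratio | Equivalent extra patients | Two-sided power, adjusted |
|---|---|---|---|---|---|
| 0.2 | 0.3 | 0.0144/1.0144 = 0.014 | 0.993 | 1% | 0.835 |
| 0.2 | 0.5 | 0.04/1.04 = 0.038 | 0.981 | 4% | 0.844 |
| 0.3 | 0.5 | 0.0525/1.0525 = 0.050 | 0.975 | 5% | 0.848 |
| 0.3 | 1.0 | 0.21/1.21 = 0.174 | 0.909 | 21% | 0.893 |
| 0.4 | 1.0 | 0.24/1.24 = 0.194 | 0.898 | 24% | 0.900 |

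Adjusted power uses 53 degrees of freedom and noncentrality (0.8/√(1−R²)) × √14 × √(1−1/55). The last factor allows for the average chance imbalance in the covariate. With R² = 0 the same formula gives 0.829, so a useless covariate costs about 0.7 of a percentage point of power.

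**3. How often the arms differ by 5 or more multiple-tract patients.** Two independent Binomial(28, p) counts: 13% at p = 0.2, 19% at p = 0.3, 22% at p = 0.4. Fixing the total among 56 patients at 16, 17 or 18 (p near 0.3) gives 14%, 24% and 15% (hypergeometric). The expected absolute difference is 2.4 to 2.9 patients.

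**4. What such an imbalance does.** Shift = (5/28) × g = 0.179 × 0.3 to 0.179 × 1.0 = 0.05 to 0.18 SD. The standard error of the arm difference is √(2/28) = 0.27 SD and the assumed design effect is 0.8 SD.

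**5. Validity of the unadjusted test.** In 40,000 simulated null trials (p = 0.3, g = 1.0) the unadjusted t-test rejected in 5.0%. Among those with at least 20 percentage points of imbalance, about 11% of the trials, it rejected in about 11%.

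**The case against.** The strongest reply is that omitting an optional covariate is not an error. Randomisation makes the unadjusted comparison valid, its standard error already allows for chance imbalance, and the simulation confirms the 5% level. That stands. A reader might infer that the primary result would be biased, and neither the documents nor the arithmetic support this.

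Second, the link from tract number to pain is an inference. Both procedures are described for a single tract, and nothing connects tract number to the extent of surgery or to VAS. That also stands. The success definition does expect that a patient may have more than one external opening, so the inference is plausible, but it remains an assumption. With g = 0.3 the gain is nil.

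Third, a reader might call a material imbalance likely. At 13-22% for 5 or more patients it is closer to one trial in five or fewer, and the shift is smaller than one standard error even at the upper end.

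Fourth, it is tempting to add seton as a second covariate because it also appears in the eligibility list. The documents give no reason to expect it to predict pain.

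Fifth, the plan says "a large effect size, 28 fistulas were required per arm" but randomises patients. If one patient can supply several fistulas, there are fewer than 28 patients per arm and the observations are not independent. The figures above would then change, and a covariate would not cure the dependence. The unit has to be settled first.

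Finally, the documents do not say that allocation used a single unstratified list, only that blocks were used. The supportable statement is that no stratum is described.

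None of this removes the practical case: the imaging is already done, and the possible gain costs almost nothing.

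**Conclusion.** The point holds as an inexpensive improvement, not as a flaw that invalidates the analysis. Tract status is imaged before randomisation, no stratum is described, and the primary VAS comparison ignores it. If 20-40% of patients have multiple tracts and their VAS is 0.3-1.0 SD higher, adjustment removes about 1-19% of the variance. Two-sided power at d = 0.8 with 28 patients per arm then moves from 0.836 to about 0.84-0.90. At the top of that range it recovers the planned 0.90 on a two-sided test without recruiting anyone. At the bottom it changes nothing.

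The conclusion rests on three assumptions: the share of patients with multiple tracts, the effect on VAS, and the reading of 28 as patients. That the factor is available before allocation and left unused rests on the text alone.

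**What to change.** In Statistical Analysis:
- Define single versus multiple tracts once. The protocol speaks of branching tracts in one place and multiple fistulas in another, so the rule should say how each is classed. Require the classification to be recorded from baseline ultrasound, or MRI where done, before allocation.
- For each primary VAS score, fit a linear model at patient level with arm and tract status. Report the adjusted mean difference with its 95% CI.
- Show the planned unadjusted t-test or Mann-Whitney result beside it, and state in advance which of the two is primary.
- State that the patient is the unit of analysis, and reconcile this with the sample size given in fistulas.

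Leave seton out unless a reason for including it is given. If recruitment is still open, a two-level stratum in Sealed Envelope is an option but not needed for the gain in precision.

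The cost is a few sentences, one recorded yes/no item and one degree of freedom of 54. If tract number does not predict pain, there is essentially no gain and a loss of under one percentage point of power.

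### The sample size counts fistulas, but the trial randomises patients and admits patients with several fistulas, so 28 per arm can mean fewer than 28 independent pain scores

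*Combined protocol and SAP*

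**What the plan says.** The Sample Size Justification states that "28 fistulas were required per arm", for an alpha of 5% and a "power of 0.9 and a large effect size". It gives no number of patients, and no other part of the protocol does.

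The rest of the design works by patient:

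- **Randomisation** (Study Participants): "Patients will randomised into the laser or ligation arm using block randomisation".
- **Eligibility** (Inclusion Criteria): the list of complex fistulas includes "Multiple fistulas; Anterior fistulas; Recurrent fistulas; Fistulas with seton". There is no limit on fistulas per patient and no rule for choosing an index fistula.
- **Primary outcome** (Study Intervention And Post-Intervention Care): "Pain scores was assessed by a blinded healthcare professional using the visual analogue scale (VAS) at 6 hours and 24 hours post operatively". Each assessment covers two conditions, resting and moving, but no score per fistula is described.
- **Analysis** (Statistical Analysis): continuous outcomes are compared by Student's t-test or the Mann-Whitney test, "with an intention-to-treat basis". No adjustment for several fistulas in one patient is mentioned.

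**The concern.** A sample size for a two-group t-test or Mann-Whitney test counts independent observations. Here that means patients: a patient with two fistulas is allocated once and gives one pain score at each time point and condition. Entering that score once per fistula would add no information and would break the independence that both tests assume.

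A target counted in fistulas equals the same target counted in patients only if every patient has exactly one fistula, and the eligibility criteria do not ensure that. If the team counts fistulas and stops at 28 per arm, the primary comparison has fewer independent scores than the calculation requires, and its power is below the stated 0.9. The intention-to-treat statement does not help: it governs how randomised patients are analysed, not how many patients a count of 28 fistulas brings in.

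**Working it through.** **Inputs from the protocol.** 28 per arm, alpha 0.05, power 0.90, a large effect size, equal arms.

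**Inputs not in the protocol (assumptions).** The numerical standardised difference d, the sidedness of the test, and the share of patients with more than one fistula. The local audit score behind the calculation is not given either.

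**Step 1: reproduce 28 per arm.** For n independent patients per arm, the two-sample t-test has 2n − 2 degrees of freedom and noncentrality d·√(n/2). Power is the probability that a noncentral t variable with these parameters exceeds the critical value (for a two-sided test, in either direction).

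- One-sided, d = 0.80: n for 90% power is 27.47, rounded up to 28. At n = 28 the noncentrality is 0.80 × √14 = 2.99, the critical value is 1.674 (54 degrees of freedom), and power is 0.905.
- Two-sided, d = 0.89: n is 27.53, rounded up to 28. The noncentrality is 0.89 × √14 = 3.33, the critical value is 2.005, and power is 0.905.

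Two-sided with d = 0.80 does not reproduce the figure; it needs 34 per arm. More generally, 28 is the smallest n that reaches 0.90 when d is about 0.792 to 0.807 (one-sided) or 0.882 to 0.899 (two-sided). In each case 28 counts independent scores.

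**Step 2: convert fistulas to patients.** If k patients in an arm have two fistulas and the rest have one, then 28 fistulas come from 28 − k patients. The two-fistula share of patients is k/(28 − k).

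**Step 3: power at the resulting number of patients.**

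| k per arm | Patients per arm | Two-fistula share | Power, one-sided, d = 0.80 | Power, two-sided, d = 0.89 |
|---|---|---|---|---|
| 0 | 28 | 0% | 0.905 | 0.905 |
| 1 | 27 | 1/27 = 4% | 0.895 | 0.894 |
| 3 | 25 | 3/25 = 12% | 0.874 | 0.869 |
| 5 | 23 | 5/23 = 22% | 0.848 | 0.839 |
| 6 | 22 | 6/22 = 27% | 0.833 | 0.822 |

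For k = 3 to 6 the loss is 0.905 − 0.874 = 0.031 to 0.905 − 0.833 = 0.072 one-sided, and 0.905 − 0.869 = 0.036 to 0.905 − 0.822 = 0.083 two-sided.

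**Step 4: is there slack?** No. Across the ranges of d in step 1, power at 27 patients per arm lies between 0.889 and just under 0.900. A single two-fistula patient per arm is enough to fall below the stated power.

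**The case against.** The best reply is that the word is a slip for patients, and the text gives that reading real support. An exclusion criterion refers to "more than 1 definitive surgery done for the fistula before", as if each patient had one fistula. The imaging step looks for a "high transphincteric fistula and/or other branching tracts", which treats extra tracts as parts of one disease. Both operations are described for a single tract. Healing requires every external opening to close, so it is judged once per patient. Consent, imaging, allocation and follow-up are all by patient, and multiple fistulas appear only as one marker of complexity. On this reading there is no loss. It may well be what was meant, but no sentence says so, and the noun changes in the one sentence that sets the trial's size.

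Two further points limit the concern. First, 28 is described as a requirement, and the protocol also gives a recruitment period (January 2018 to December 2020). It nowhere says that recruitment stops at 28 fistulas, so a loss needs both a fistula count and a stop at that count. Second, the shares in the table are illustrations without a source in the protocol, and the smallest departure costs only about one percentage point. Both are right, and they are why the point is minor. Neither makes the stated unit correct.

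It is also true that the missing effect size, standard deviation and sidedness are a larger gap in the same section. That is a separate matter. Changing the noun would not verify the audit figure, particularly if the audit was tabulated by fistula.

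**Conclusion.** The point holds as a minor one: the target is stated in the wrong unit for the randomisation, the primary outcome and the planned tests. The loss is zero if fistulas means patients. If the target is applied literally and recruitment stops there, power falls by about one percentage point with one two-fistula patient per arm, and by about 3 to 8 points if 12% to 27% of patients have two fistulas. These sizes rest on assumed shares and on the two assumed calculations that reproduce 28 per arm. The direction needs no assumed share: any patient who contributes more than one fistula to the count reduces the number of independent scores.

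**What to change.** In the Sample Size Justification, give the target as 28 patients per arm (56 in total). In the Statistical Analysis, add that every outcome is analysed with one record per randomised patient at each time point and, for pain, in each condition (rest and movement), however many fistulas the patient has.

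The cost is two sentences. If patients were meant all along, recruitment does not change. If fistulas were being counted, the scenarios above imply 1 to 6 more patients per arm than that count would give, and no more than the calculation already requires.

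### The plan is labelled intention-to-treat but has no rule for missing 6-month outcomes, so healing, Wexner and SF-36 become complete-case comparisons by default

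*Combined protocol and SAP*

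**What the plan says.** The Statistical Analysis section sets the analysis "with an intention-to-treat basis" and does not define the term further. For categorical outcomes: "Differences between groups can be compared using chi-square analysis or the Fisher exact test when data is categorical". For the rest: "continuous variables can be compared using the student t-test or Mann-whitney based on normality of data distribution". The only inferential criterion is p below 0.05.

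Under Study Definitions And Outcome Measures, healing requires closure "in combination with the cessation of outflow from the external openings at 6 months post operatively". The counterpart reads: "Surgical failure was defined as failure of the fistula to close with persistence of discharge at 6 months post operatively". The same paragraph says failure covers wound infection, recurrence and technical failure.

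Under Study Intervention And Post-Intervention Care, there is a wound review at one week and then "an official surgical consult at 1 month and 6 months post operatively". On content: "Each surgical consult involved a history taking, clinical examination, QOL and continence assessment". A suspected recurrence before 6 months leads to endo-anal ultrasound.

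The Secondary Outcome Measures list gives a different schedule: "Continence assessed using Wexner at 0-, 3- and 6-months post-surgery", with the same times for SF-36. Healing does not appear in that list or as the primary outcome.

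The documents contain no rule for a missing 6-month outcome, no imputation or repeated-measures model, no sensitivity analysis and no dropout allowance.

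**The concern.** Intention-to-treat means that every randomised patient counts in the allocated arm. The named tests respect allocation, but they can use only patients who have a value. A patient who misses the 6-month consult is neither healed nor failed under the definitions and, with no rule to say otherwise, leaves the denominator. Wexner and SF-36 are collected at the same consults, so one missed visit removes all three outcomes.

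Whether a patient returns is plausibly related to healing, in either direction: a healed patient may see no reason to come back, and a patient whose fistula persists may go elsewhere. If that relation differs between laser and LIFT, the complete-case difference is biased, and the intention-to-treat label hides it.

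A second weakness adds to this. With only a p-value reported, a non-significant healing result in a trial of this size could be taken as equal healing and set beside a pain result that favours one operation.

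**Working it through.** **Inputs.** From the documents: 28 per arm, alpha 5%, power 0.9, a large effect size. Assumed, because the documents give nothing: the effect size d = 0.8, the number missing, the true healing rates, and one fistula per patient (the sample size counts fistulas, and patients with multiple fistulas are eligible).

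**1. The plan's own figure.** A two-sample t-test with d = 0.8, alpha 0.05 and power 0.90 needs 27.5 per arm one-sided, so 28, and 33.8 two-sided, so 34. The stated 28 therefore reproduces as a one-sided test with nothing added for loss. Allowing 10% loss gives 28/0.9 = 31.1, so 32; allowing 20% gives 28/0.8 = 35. Sidedness is a separate matter. What counts here is that no margin for missing outcomes was built in.

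**2. Healing rate within one arm.** With true healing p, and fractions mH of healed patients and mF of failures missing, the complete-case rate is p(1−mH) / [p(1−mH) + (1−p)(1−mF)]. At p = 0.70:
- Pattern A, mF = 0.30 and mH = 0.05 (overall loss 0.7×0.05 + 0.3×0.30 = 12.5%): 0.665/(0.665 + 0.210) = 76.0%.
- Pattern B, mF = 0.05 and mH = 0.30 (overall loss 0.7×0.30 + 0.3×0.05 = 22.5%): 0.490/(0.490 + 0.285) = 63.2%.

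**3. Difference between arms, same pattern in both.** For true 70% v 50% (20 points):
- Pattern A: 76.0% v 0.475/(0.475 + 0.350) = 57.6%, a difference of 18 points.
- Pattern B: 63.2% v 0.350/(0.350 + 0.475) = 42.4%, a difference of 21 points.

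For true 70% v 70% the difference is 0 under either pattern.

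**4. Difference between arms, opposite patterns.** With true 70% in both arms, pattern A in one and pattern B in the other gives 76.0 − 63.2 = 12.8 points where the truth is 0. In the extreme, where one arm loses only healed patients and the other only failures, m missing per arm gives a spurious difference of m/(28−m): 7.7, 12.0 and 27.3 points for m = 2, 3 and 6.

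**5. Bounds on all randomised patients.** With 4 missing per arm and an observed 19/24 v 15/24, the complete-case difference is 79.2 − 62.5 = 16.7 points.
- Lower bound (missing not healed in the first arm, healed in the second): 19/28 − 19/28 = 0.
- Upper bound (the reverse): 23/28 − 15/28 = 8/28 = 28.6 points.
- All missing counted as not healed: 19/28 − 15/28 = 4/28 = 14.3 points.

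**6. What a bare p-value conveys, even with all 28 observed.** Exact power of Fisher's test for 70% v 50% is 24%. The 95% half-width for the difference, 1.96×√(2p(1−p)/28), is 25.7, 24.0 and 21.0 points at p = 0.6, 0.7 and 0.8.

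**7. Counting every missing patient as not healed.** Under pattern B, 70% reads as 0.7×0.70 = 49% and 50% reads as 0.5×0.70 = 35%. The difference is 14 points against a true 20, where the complete-case difference is 21.

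**The case against.** The strongest reply is that the plan never restricts analysis to patients seen at 6 months. Chi-square and Fisher tests work equally well on all randomised patients once missing outcomes are assigned, so complete-case analysis is inferred from silence. That is right: it is the default, not a stated rule.

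A reader might go further and infer that the healing comparison will be biased. The documents do not support that. They give no attrition rate, and step 3 shows that the same loss pattern in both arms leaves the difference almost unchanged. A reader might also infer that counting every non-attender as not healed would restore intention-to-treat. Step 7 shows that this can do worse than complete-case analysis, so it cannot be the only rule.

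Three further points stand in part. Some early failures may be known from imaging for suspected recurrence, but no sentence says they count if the 6-month consult is missed. Healing is not a listed outcome, although it is defined under a heading on outcome measures. The power and interval widths in step 6 have nothing to do with missing data, and the plan makes no claim of equal healing; they support reporting an interval, not the missing-data point.

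**Conclusion.** The point holds as a gap in specification: the label and the named methods agree only if nobody is lost by 6 months. It concerns healing, Wexner and SF-36. The primary pain outcome is measured at 6 and 24 hours and is little exposed to clinic non-return.

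The size depends on assumed attrition. At 4 missing per arm, the difference between arms is uncertain by 28.6 points before any sampling error. A biased difference requires loss that is related to healing differently in the two arms, which the documents neither show nor rule out. The figures also assume one fistula per patient. The change is worth making before outcomes are examined, because a missing-data rule chosen afterwards can be chosen to suit the result. It does not threaten the trial's main question.

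**What to change.** Amend the Statistical Analysis section as follows.

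1. **Healing, estimate.** Report the 6-month difference in healing proportions (laser minus LIFT) with a 95% confidence interval beside the p-value. State that a non-significant result will not be read as equal healing.
2. **Healing, missing outcomes.** Show results with all randomised patients as the denominator under best-case and worst-case assignment. Count failures documented before 6 months as failures. Label the complete-case result as such. Keep counting all missing patients as not healed as one sensitivity analysis, not the sole primary rule. Say whether the unit is the patient or the fistula.
3. **Wexner and SF-36.** Use a repeated-measures mixed model with baseline and every recorded visit, so that a patient without a 6-month score still contributes. This assumes that the recorded scores account for the missingness, which should be stated. Add a rank-based or bootstrap check for skewed Wexner scores. First reconcile the 3-month assessment in the Secondary Outcome Measures with the 1-month consult in the follow-up text, since the model's visits cannot be specified until that is settled.

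The cost is plan wording, a few extra analyses and wider stated uncertainty on healing. No added patients are needed for these analyses.
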